SKY currently offers insurance to households in several rural districts in Takeo and Kandal provinces, and has recently expanded into the capital, Phnom Penh, targeting specific groups such as garment workers and market vendors. In December 2005, the program had 4,392 beneficiaries from 917 households, up over 160% from the previous year. Take-up of insurance ranges from 2% in regions where insurance has been only recently introduced to 12% in the longest served regions (SKY briefing note, 2005).

We will study SKY's 2007-8 expansion into additional districts in Takeo and Kandal provinces as well as parts of Kampot. We will evaluate the health and economic effects of the SKY program on households using a **randomized controlled trial.** The central methodological tool of this evaluation is randomized distribution of "Lucky Draw" coupons that will induce random variation in the likelihood of taking up insurance. Randomization allows estimation of the causal effects of health insurance as distinct from all other characteristics that vary across insured and non-insured households. We will also use in-depth interviews of a small group of households in selected villages to take a closer look at household behavior. Finally, interviews with households, health center staff, and SKY Member Facilitators will help to understand SKY's effects on health centers.

2. Objectives of the Study

The research has four objectives:

1. To estimate the causal effect of health insurance on households.

- Economic outcomes (e.g., medical spending; sales of productive assets; household debt and loans)

- Health outcomes (e.g., frequency and duration of illness; subjective self-health assessments; objective health measures)

- Health utilization (e.g., public health facility utilization; substitution to public facilities from private health centers and traditional medicine; preventative care utilization; timely utilization of curative care; self-medication)

2. To understand the determinants of take-up of health insurance; the extent of adverse and positive selection; the potential for risk-pooling.

- Household characteristics (e.g., wealth and income; age and sex composition; past health utilization; health status; perceptions of public facilities; expected utilization of public facilities; access to alternate sources of health financing; risk aversion)

- Public health facility characteristics (e.g., objective measures of quality; convenience of access)

3. To identify potential effects of health insurance on public health facilities (e.g., hours and drug availability; subjective and objective quality indicators).

 To contribute to the body of knowledge on health insurance in Cambodia and in developing countries more broadly.

3. Research Design

We will use a mix of qualitative and quantitative methods, including both in-depth interviews of SKY employees, health care providers and households and a large household survey.

The large household survey will measure the impact of insurance on rural Cambodians. To overcome the key obstacle to causal inference—that those who choose to purchase insurance typically differ in many observable and unobservable ways from those who do not—we will implement a randomized controlled trial that allows us to identify the impact of health insurance independently from all other factors that may affect a household's decision to take up insurance. No household will be denied access to insurance. Rather, by subsidizing the premium of a randomly selected group of households, we can estimate the effect of insurance on households without substantially altering the existing SKY program. The study design will also enable us to examine characteristics of the groups that buy or decline insurance at different prices. Using data from the baseline survey, we will examine the characteristics (in particular, health status and prior health care utilization) of those who choose to purchase health insurance at different prices. Using data from the follow-up survey, we will also compare the utilization rates of people who buy insurance at different prices, and compare the dropout rates of those who utilize facilities at different rates. Both techniques allow us to estimate the extent and nature of self-selection.

The randomized evaluation will be implemented as SKY visits villages to promote insurance. When the SKY program first rolls out into a region, SKY holds a village meeting to describe the insurance product to prospective customers. At

the end of each meeting, SKY will hold a Lucky Draw lottery in which a random subset of households receives coupons for discounts on the insurance premium.

The randomization of premiums will provide a discount to some households. Of households that attend the village meeting, 20% of households, up to a maximum of 12 households per village, will win a coupon for 5-months free insurance in the first 6-month cycle, with the option to renew for a second 6-month cycle with a coupon for 3-months free. The remaining households in attendance at the meeting will be entitled to a coupon for a 1-month discount on insurance, which is the usual policy for the SKY program. SKY will be holding village meetings in Takeo, Kandal, and Kampot provinces over the course of the thirteen months from November 2007 to December 2008 (roughly the period during which the baseline survey will be administered). Table 1 shows an approximation of the distribution of the targeted sample across regions. The column "Total Meetings Held" indicates the number of village meetings SKY plans to hold in each district or province and "Total Lucky Draws" indicates the number of Lucky Draws held in the given district. The final column, "% of Villages Surveyed", indicates the approximate percentage of the sample that will come from each area. Note that we will hold Lucky Draws at most village meetings in 2008. We will only survey villages in which we hold a Lucky Draw.

				Total	Total	% of Villages	
				Meetings	Lucky	Surveyed	
				Held	Draws		
Takeo Province			128	128	51%		
Ang Roka village	s (older	villages)		32	32	13%	
Kirivong villages			48	48	19%		
Donkeo villages				48	48	19%	
Kandal Province	74	72	29%				
Koh Thom village	es			74	72	29%	
Kampot Province	50	50	20%				
Kampot villages				50	50	20%	
All Villages				252	250	100%	

Table 1: Targeted Regions

In addition to the randomized intervention, we will also be studying the effect of SKY on the quality and functioning of public health facilities. The fact that higher quality facilities are targeted by SKY means that there can be no valid control group in a longitudinal study, but we will use several methods to measure changes in health center quality over time that will allow us to gain some insight into the impact of SKY.

4. Sampling Strategy

For the quantitative survey, the main evaluation sample will consist, roughly, of half coupon winners and half non-winners. More precisely, we will interview all large coupon winners, and randomly select an equal number of small coupon winners to interview. In addition, to address the question of selection into insurance, we will oversample households that purchased insurance from the population of small coupon winners. In total, our sample of approximately 5,200 households will consist of approximately 46% large coupon winners and 54% small coupon winners. For the quantitative survey, the main evaluation sample will consist, roughly, of half coupon winners and half non-winners. More precisely, we will interview all large coupon winners, and randomly select an equal number of small coupon winners to interview. In addition, to address the question of selection into insurance, we will oversample households that purchased

insurance from the population of small coupon winners. In total, our sample of approximately 5,200 households will consist of approximately 46% large coupon winners and 54% small coupon winners¹.

The survey team will interview households between two and seven weeks after the village meeting². An Evaluation Representative will attend each village meeting to help run the Lucky Draw lottery. At the end of each village meeting the Evaluation Representative will randomly select a number of the small coupon winners to be interviewed. SKY Insurance Agents will visit these households, as well as all large coupon households, before the 21st of the month. Once all households have had the opportunity to purchase insurance, we will interview these sampled households. Table 2 offers a breakdown of the interview sample.

	Large coupon wi	inners S	Small coupo	n winners	Additional small coupon	Total
	(100% sampled)		(25% sampled) buyers		(50% sampled)	
	1	2	3	4	5	6
	Total	Buyers (est.)	Total	Buyers (est.)	(Estimated)	(Estimated)
Per meeting	9.5	3.8	9.5	0.57	1.8	20.8
Total	2,375	950	2,375	143	453	5,203

Table 2: Quantitative survey sample

Notes: We assume 250 village meetings. Based on the results from the pilot test in 2007, we assume 40% of large coupon winners purchase SKY and 6% of small coupon winners purchase SKY.

Columns [1] and [3] of Table 2 show the number of large and small coupon winners to be interviewed, respectively. Columns [2] and [4] show the number of buyers that will be interviewed out of those two groups, with sample sizes estimated based on the winter 2007 pilot take-up rates. Column [5] shows the estimated number of additional small coupon buyers we will oversample. Finally, column [6] shows the total number of households interviewed per village and overall.

¹ Actual number and distribution (buyers/non-buyers, etc.) of households will vary depending on village meeting attendance and take-up in each village.

5. Methodology

In this section we detail the four sources of data that will be collected in the evaluation, namely, the household survey, village leader interview, village monographs, health center surveys and health logbooks.

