To measure selection into insurance, we will run five sets of analyses. First, we will look at average baseline characteristics of households that buy SKY and compare them to those who don't buy SKY. We will also run a logistical regression to determine the impact of each indicator on the purchase of insurance (where decision to purchase (0 or 1) is on the left- hand side and household and health facility quality characteristics are on the right-hand side of the equation).

Second, we will compare characteristics and average health care utilization of households that buy SKY at different prices, to examine whether a lower price induces more risk pooling (that is, attracts a healthier applicant pool).

Third, we will use external sources of data—the Cambodia Demographic Health Survey (DHS) and 2008 Census —to compare the profiles of village members who attend SKY village meetings and of SKY members to the general population (at the national, provincial and possibly district level). In the household survey our demographic measures (household size and members' age and sex) and some of our health (e.g., body mass index, that is, weight for height) and socioeconomic status (e.g., education) data are directly comparable to the DHS.

Fourth, we will examine selection using SKY data on membership and member utilization of health facilities. To

illustrate the possibilities, in 2007 all but one of the SKY members who had used a health center at least once renewed their membership, which was a far higher renewal rate than among those who had not used a facility at least once. This is a simple analysis using incomplete data, but illustrates the potential for such data to provide important insights into who is keeping and who is dropping insurance.

Finally, the Village Monograph will give us an in-depth qualitative study of how households make the decision to purchase insurance, how they use health facilities differently when covered by it, and how they decide to renew or drop insurance—all of which help us understand selection into the insurance market.

B. Predictors of Take-up

We will use the following measures that are collected using the household survey (described above) to predict take-up of SKY insurance:

• Wealth/income indicators (e.g., a wealth index created by asset ownership)

 Demographic characteristics of the household (age of members, number of members, gender and age of head/primary decision-maker, etc.)

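### Because of the 12-coupon cap, the chance of a large coupon depends on meeting attendance, so comparing buyers at different prices across villages mixes price with attendance

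*Protocol*

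**What the plan says.** Section 3 (Research Design) sets the lottery: "20% of households, up to a maximum of 12 households per village, will win a coupon for 5-months free insurance". For everyone else, "The remaining households in attendance at the meeting will be entitled to a coupon for a 1-month discount on insurance". The cap applies to the first group only.

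Section 4 (Sampling Strategy) builds the survey sample in two parts. For the main sample, "we will interview all large coupon winners, and randomly select an equal number of small coupon winners to interview". A second part is added for the selection question: "to address the question of selection into insurance, we will oversample households that purchased" insurance, taken from the small-coupon group. Table 2 gives the planned numbers: "Per meeting 9.5 3.8 9.5 0.57 1.8 20.8" (large winners, their buyers, small winners drawn, their buyers, additional small-coupon buyers, total). Its note reads "We assume 250 village meetings", with take-up of 40% (large) and 6% (small). The column labels give sampling shares of 100%, 25% and 50%. Footnote 1 says that actual numbers will vary with attendance.

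The comparison at issue appears twice. Section 3 says "we will also compare the utilization rates of people who buy insurance at different prices". The statistical methods for Objective 2 say "Second, we will compare characteristics and average health care utilization of households that buy SKY at different prices", in order to see whether a lower price attracts a healthier pool. Neither place mentions the village, the coupon probability or the sampling fraction.

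**The concern.** Coupons are drawn separately at each meeting, so price is randomised within a village. Across villages, price is independent of village only if the chance of a large coupon is the same everywhere. The cap breaks this in larger meetings: large-coupon buyers stop increasing at 12 winners, while small-coupon buyers go on increasing with attendance.

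The equal-number draw restores the balance in the main sample. It does not do so for the buyer oversample, which was added for the selection question. If well-attended meetings take place in villages that differ in access, wealth or use of facilities, part of that difference will show up as a difference between buyers at the two prices. It would then be read as price-driven selection, which is what this analysis is meant to detect.

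**Working it through.** **1. The plan's own figures.** Inputs are from Table 2 and its note. Small-coupon households per meeting: 9.5 / 0.25 = 38. Attendance: 38 + 9.5 = 47.5. Winners: 20% of 47.5 = 9.5, and 9.5 × 250 = 2,375, as stated. Large-coupon buyers: 0.40 × 9.5 × 250 = 950, as stated. Small-coupon buyers in the matched draw: 0.06 × 9.5 × 250 = 142.5, stated as 143.

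Column 5 does not reproduce. At its 50% label, 0.5 × 0.06 × (38 − 9.5) = 0.855 per meeting, or 214 in total, against 1.8 and 453. Taking all remaining buyers gives 1.71 per meeting, or 428.

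**2. Threshold.** 12 / 0.20 = 60 attending households.

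**3. Effect of attendance N.** Let L = min(0.2N, 12). Large-coupon buyers are 0.40L. Surveyed small-coupon buyers are 0.06L (matched draw) plus 0.5 × 0.06 × (N − 2L) (oversample at the label).

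| N | Chance of large coupon, L/N | Small winners drawn, L/(N − L) | Large : small surveyed buyers | Large share, surveyed buyers | Large share, all buyers |
|---|---|---|---|---|---|
| 47.5 | 20% | 25% | 3.8 : 1.425 | 72.7% | 62.5% |
| 60 | 20% | 25% | 4.8 : 1.80 | 72.7% | 62.5% |
| 80 | 15% | 17.6% | 4.8 : 2.40 | 66.7% | 54.1% |
| 100 | 12% | 13.6% | 4.8 : 3.00 | 61.5% | 47.6% |
| 150 | 8% | 8.7% | 4.8 : 4.50 | 51.6% | 36.7% |

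Up to 60 the ratio is constant and pooling does no harm. In the matched sample alone the large-coupon share of buyers is 0.40 / 0.46 = 87.0% at every N. The last column shows that weighting by survey sampling fractions alone is not enough: even with every buyer counted, the ratio still changes with N, because assignment itself is unequal.

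**4. How much of the comparison is unmatched.** By Table 2, 453 / (143 + 453) = 76% of small-coupon buyers come from the oversample. At the 50% label it would be 0.855 / 1.425 = 60%. It is the larger part either way.

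**5. Possible size.** The documents give no spread of attendance, so this step is an assumption: lognormal attendance, scaled so that mean winners equal 9.5, with the 50% oversample. The false difference is (share of small-coupon buyers from capped meetings − share of large-coupon buyers from them) × the trait gap between capped and uncapped villages. SE = √(1/950 + 1/n_small). At CV 0.5, (0.550 − 0.461) × 0.5 = 0.045 SD, SE = √(1/950 + 1/427) = 0.058, z = 0.77, and a 5% test rejects 12% of the time.

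| CV | Mean N | Cap binds | From capped meetings: large / small buyers | False difference, 0.5 SD gap | Rejection, 0.5 SD gap | Rejection, 0.2 SD gap |
|---|---|---|---|---|---|---|
| 0.2 | 48.2 | 11% | 14% / 16% | 0.006 SD | 5.1% | 5.0% |
| 0.3 | 50.2 | 22% | 28% / 32% | 0.019 SD | 6.1% | 5.2% |
| 0.5 | 57.0 | 36% | 46% / 55% | 0.045 SD | 12% | 6.1% |
| 0.7 | 66.9 | 44% | 56% / 69% | 0.064 SD | 21% | 7.5% |

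If every meeting had 47.5 attenders, or if buyer traits did not vary with attendance, the bias would be zero. With all remaining buyers surveyed, the CV 0.5 figure rises from 0.045 to 0.054 SD. The rejection rates ignore village clustering.

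**The case against.** The strongest reply is that the protocol nowhere commits itself to an unadjusted pooled comparison. A reader might infer one from the plain mention of averages by price, but the text only names no village adjustment, and an analysis plan not shown could supply one. That stands as a limit on the charge. What remains is that the protocol itself fixes a capped lottery, an unmatched oversample and a comparison by price, and these fit together only if the comparison respects the village draw.

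Village features are also not ignored. Section 5.2 intends village-leader data for the selection study, the take-up predictors include distance and facility quality, and the appendix plans for clustering. These help, but they are not tied to the price comparison, and clustered standard errors do not remove a bias.

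On size, the objection largely stands. The 12-21% rejection rates need both a wide spread of attendance and a 0.5 SD gap, and the documents give neither. Those scenarios also need mean attendance of 57-67, against the 47.5 that Table 2's 25% implies. In the other direction, a reader might infer from the 453 additional buyers that the cap binds often: at the 50% label they imply attendance of 453/250/0.03 + 19 = 79.4. Sampling nearly all remaining buyers explains that figure about as well, so it proves nothing.

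The Table 2 heading is a small matter. The operative rule is already an equal-number draw, and nothing in the protocol builds weights from 25%.

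**Conclusion.** The mixing of price with attendance follows directly from the coupon and sampling rules wherever more than 60 households attend. It touches one of the five selection analyses under Objective 2, and the related utilization comparison in section 3. Its size cannot be fixed from the documents: under the stated assumptions it runs from negligible (0.006 SD at CV 0.2) to noticeable (0.064 SD at CV 0.7) with a 0.5 SD gap, and it stays slight with a 0.2 SD gap. It needs both variable attendance and a link between attendance and buyer traits. The relevant quantity is attendance at the meeting, not village population.

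A reader might infer that the intention-to-treat or instrumental-variable estimates are biased too. The documents do not support that: the main sample is matched 1:1 within each meeting, and the Objective 1 regression has individual fixed effects.

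**What to change.** In the second analysis under Objective 2, and in the matching sentence of section 3, state that buyers at different prices are compared within village (village strata or fixed effects). Alternatively, state that they are weighted by the inverse of both the village-specific coupon probability and the village-specific sampling fraction. Keep attendance, winners, households drawn and buyers for each village. As a minor edit, mark the 25% in Table 2 as holding only where the cap does not bind, so that it is not later used as a flat weight.

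The cost is a line of wording and the keeping of counts that arise at each draw and sale. The within-village form drops villages without buyers at both prices. At 3.8 and 1.425 expected buyers (Poisson, 50% label) that is 1 − (1 − e^−3.8)(1 − e^−1.425) = 26% of villages, with a standard error about 10% larger. At Table 2's own 0.57 + 1.8 = 2.37 small-coupon buyers it is about 11% of villages. The weighted form avoids this loss of villages.

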5.1. Household Survey

The principal component of data collection is a large-scale survey collecting three rounds of quantitative data from approximately 5,200 households. The sampling is described above in section 4 of this protocol.

The baseline will be a rolling survey, administered to each village approximately two to seven weeks after the Lucky Draw is held³. The second round will use the same rolling format, and will be administered 12 months after the baseline. The final survey round will be administered 24 months after the baseline.

This survey will collect data on household demographics, wealth indicators, self-perceived and objective health measures, health care utilization and spending, assets and asset sales, savings, debt, health risk behaviors, willingness to take financial risks, trust of institutions, means of paying for large health expenses, and willingness to trade current for future income. We describe the elements of this survey in detail in Section 6, below.

The survey will ensure high quality data using multiple means. All surveys will be reviewed at the household by the enumerator. All surveys will then be reviewed by a data editor who reviews unclear responses and outliers and checks for data consistency (e.g., mothers who are male or age 7). All surveys will then be reviewed by a field supervisor. The field editor and supervisor also review a subset of questions with a subset of households to check on data quality. These checks will include all very large responses for high health care costs (an important point, as health care costs are dominated by a small number of outliers.) When data are entered, we run a further set of checks for consistency and permissible values. Unexpected answers and outliers lead to rechecking the paper questionnaires.

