5.2. Village Leader Interview

In each village, we will interview the village chief or village leader in order to collect general village-level information, including the location of all local health facilities (public, private, pharmacies, traditional healers, etc.), recent villagelevel shocks (drought, flood, epidemics, etc.), availability of lending institutions, seasonal access to roads and price and availability of paid transportation. Because the randomization is at the household level, the information garnered from the village leader will be of greatest use in the selection study (e.g., testing if villages far from regional hospitals have lower take-up), in assessing the external validity of the evaluation, and potentially in estimating the effect of insurance in villages with different characteristics.

³ See previous footnote: the timelag between village meetings and interviews will be longer for households attending earlier village meetings.

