6.1. Statistical Methods

To estimate the causal effect of health insurance on household health and economic outcomes, we will implement a number of estimators. The overall econometric technique is to generate multiple estimates of the effect of insurance on the outcomes of interest, thus allowing us to construct a credible range of the estimated program effect. To begin with, we will construct a lower bound for the program effect the Intention-to-Treat effect. Here, outcomes at baseline will be differentiated from outcomes in the follow-up, across large and small coupon winners. This estimate provides a credible lower bound for the true program effect, because many of the large coupon winners will not take up insurance, while some of the small coupon winners will, yielding an underestimate of the true program effect. Formally, we will run a regression that includes a vector of individual fixed effects (individuali) to absorb characteristics of the household or individual, observed or unobserved, that do not change over time and a vector of year fixed effects (year t) to control for changes over time that affect all individuals (or households). We can also control for

This section outlines our methodology for achieving each goal. For objectives 1 through 3, we include a list of indicators that we plan to measure using our survey instruments. Note that the final list of indicators will depend on pre-test results, and on the power we have to measure SKY impacts using each indicator with the given study design.

Methodology for Objective 1: The Causal Effect of Health Insurance

J and I time-variant individual- and household-level covariates (Xjt and Zjit) that might affect health, health care utilization, and other outcomes, e.g., current household income. Thus, we can estimate:

Yjivt = β postit * large-couponi + γ postit + Σ li=1 α Xit + Σ Jj=1 δ Zjit + individualj+ yeart + Uvt + ϵ jivt

In this specification, postit indicates follow-up observations, Uvt represents village-level shocks collected in the village leader survey, and ɛjivt is a random error term representing individual variation from the mean. The coefficient β is the difference-in-differences estimate of the effect of being offered a high-value coupon. Outcome indicators (the Yjivt in the equation above) for Objective 1 are listed below.

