Suppose now that instead of just having observations at one point in time, or at two points in time for different groups of households, we have observations on the same households both before and after they receive a coupon. This type of data is called panel data. In that case, we can use fixed effects to improve the accuracy of our estimates. Essentially, what we are doing is allowing each household to have a unique baseline level of utilization. Thus, the effect of insurance is assumed to be equal for each household, but the regression line represented by the basic regression equation is raised or lowered for each household (i.e., the intercept is different for each household).

For example, if we have panel data we can take our difference-in-differences estimate from equation (5) and add fixed effects. Below, i represents a household and t represents time.

(7) utilizationit = β_0 + β^* couponit + γ^* 2001 + δ^* 2001*couponit + household_i + εit

In the above equation, we use the difference-in-difference equation, but allow each household to have a unique (fixed) baseline level of the outcome. Essentially, what we are doing is including a variable representing each household. Thus, **household** represents not just one variable, but an entire vector of variables. Adding household fixed effects will give us a more accurate estimation of the variable of interest, δ in equation (7), since we are reducing variance due to fixed household differences.

As in equation (5), we can add additional variables to the

right-hand side of equation (7) that we think will have an effect on utilization. Fixed characteristics of households will be taken care of by the household fixed effects, but we can add household characteristics that vary over time.

d. Clustering

Finally, when we run the regression we will want to take into account clustering of observations. Clustering of observations occurs when certain observations are more similar to each other than other observations. For example, households that are located within the same village may be more similar, and may experience more similar shocks (economic, health, etc.) than households in a different village. In the same way, individuals who live in the same household may be more similar to each other than individuals in other households. If we do not correct for clustering, standard errors will appear artificially low, leading us to overestimate the accuracy of our coefficient estimates.

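### The baseline survey follows the coupon draw and the purchase opportunity, so the Section 6.1 difference-in-differences ITT can subtract early effects from 4-week-recall and current-status outcomes

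*Protocol*

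**What the plan says.** **Schedule.** Section 4 has the Lucky Draw at the village meeting, followed by a sales visit: "SKY Insurance Agents will visit these households, as well as all large coupon households, before the 21st of the month". The interview comes next: "Once all households have had the opportunity to purchase insurance, we will interview these sampled households". Section 5.1 gives the interval: "The baseline will be a rolling survey, administered to each village approximately two to seven weeks after the Lucky Draw is held". Footnote 3 adds that "the timelag between village meetings and interviews will be longer for households attending earlier village meetings", without saying by how much. The notes to Table 2 give the purchase gap expected by then: "we assume 40% of large coupon winners purchase SKY and 6% of small coupon winners purchase SKY". The date on which cover begins is not stated.

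**Estimator.** Section 6.1 defines the ITT so that "outcomes at baseline will be differentiated from outcomes in the follow-up, across large and small coupon winners". The regression has individual fixed effects, and its coefficient of interest is on the product of the follow-up indicator and the large coupon. Section 6.1 calls the result a lower bound, and gives imperfect take-up in the two groups as the only reason.

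**Premise.** The Statistical Appendix explains the method with pre-lottery data. Table 4 has a row of visits before the lottery. Equation (5) reads the coupon main effect as a difference that existed beforehand. Part c motivates fixed effects with a case in which "we have observations on the same households both before and after they receive a coupon".

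**Recall.** Sections 6.2.1, 6.3.1 and 6.4.1 use four weeks for all incidents and 12 months for major incidents. Debt status, perceived health, activities of daily living, water practices and knowledge are current-status items.

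**The concern.** Difference-in-differences with unit fixed effects recovers the effect of the offer only if the first measurement is free of that effect. Here the first measurement follows both randomisation and the purchase decision, when the arms are expected to differ by 40% − 6% = 34 points in insurance purchase. Whatever the coupon or the cover has already done to an outcome enters the baseline and is removed from the estimate. Rounds 2 and 3 are both compared with this baseline, so both are exposed.

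Nothing else in the protocol supplies a measurement from before the draw. The logbooks of Section 5.5 would be handed out at the baseline survey itself.

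The timing also touches Objective 2. Perceived facility quality, trust and similar attitudes are entered as predictors of purchase but are asked after it. The text on Objective 3 itself allows that joining SKY may change what members expect of health centres.

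**Working it through.** **Inputs.** Interview at t = 2 to 7 weeks after the draw (Section 5.1). Recall window R = 4 or 52 weeks (Section 6.2.1). Assumptions: t is spread evenly over 2 to 7 weeks, and cover starts c weeks after the draw, with c = 2, 4 or 6.

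**The plan's own example.** The protocol gives no figure for this bias. Table 4 can serve as a scale. Its after-lottery difference is 2.5 − 1.03 = 1.47, rounded there to 1.5, and 1.5 / 0.5 = 3. That calculation does not subtract a baseline.

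**Step 1: share of the baseline window after the draw = min(t, R) / R.**
- R = 4: 2/4 = 50% at week 2, 3/4 = 75% at week 3, 100% from week 4. The mean is [(16 − 4)/8 + 3] / 5 = 4.5/5 = 90%.
- R = 52: 2/52 = 3.8% at week 2, 7/52 = 13.5% at week 7. The mean is 4.5/52 = 8.7%.
- Current-status items: 100%.

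In villages with a longer lag, each further week adds 1/52 = 1.9 points to the 12-month share.

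**Step 2: share of the 4-week window already under cover = mean of min(max(t − c, 0), 4) / 4.** The second column of shares is 90% less the first.

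| Cover starts after draw | Under cover | After draw, before cover |
|---|---|---|
| 2 weeks | 60% | 30% |
| 4 weeks | 22.5% | 67.5% |
| 6 weeks | 2.5% | 87.5% |

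For 12-month recall, the covered shares are 4.8%, 1.7% and 0.2%.

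**Step 3: effect on the estimate.** Let k be the effect during the exposed part of the baseline window, as a fraction of the follow-up effect. Then E[DiD] = ITT × (1 − share × k). With ITT = 1.5 and an effect only while under cover:

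| Cover starts | k = 0 | k = 0.5 | k = 1 |
|---|---|---|---|
| 2 weeks | 1.5 | 1.5 × (1 − 0.30) = 1.05 | 1.5 × (1 − 0.60) = 0.60 |
| 4 weeks | 1.5 | 1.5 × (1 − 0.1125) = 1.33 | 1.5 × (1 − 0.225) = 1.16 |
| 6 weeks | 1.5 | 1.5 × (1 − 0.0125) = 1.48 | 1.5 × (1 − 0.025) = 1.46 |

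If the effect starts at the draw (share 90%), 4-week outcomes give 0.83 at k = 0.5 and 0.15 at k = 1. This is the outer limit. For 12-month recall (share 8.7%), the same calculation gives 1.44 and 1.37.

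The sign can reverse. Suppose large-coupon households put off care before cover starts, with k = −0.25 on the 67.5% pre-cover share for c = 4 and no effect yet under cover. Then the estimate is 1.5 × (1 + 0.675 × 0.25) = 1.75, which is inflated.

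**The case against.** Several replies have force, and they limit the point.

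- **Many outcomes use 12-month recall.** Major incidents, health loans and forgone treatment do. For these, 86% to 96% of the baseline window still precedes the draw. Stunting is also unlikely to move within two to seven weeks. This stands.
- **The instrumental-variable estimate does not subtract the baseline.** Equations (2) to (4) use outcome levels with the coupon as instrument. This stands. A reader might infer that the local average treatment effect is biased too, but the equations do not support that. It would inherit the problem only if someone divided the difference-in-differences ITT by the first stage.
- **The fixed-effects passage is a tutorial.** The words about seeing households before the coupon belong to a supposed example, and Table 4 is labelled illustrative. So the appendix does not assert that this study has a pre-coupon survey. But the Section 6.1 regression needs that premise, and part b applies equation (5) to the coupon randomisation of this study.
- **Cover cannot be assumed from the day of the draw.** Agents sell afterwards. A reader might conclude that households have more cover in the baseline window than at round 2, so that the contrast reverses. That needs cover from the draw or soon after and an end at exactly 52 weeks without renewal, and the protocol states neither.
- **Most take-up predictors are anchored at or before purchase.** Past utilisation, past shocks and health at the purchase date are. Only attitudes and perceptions are exposed.

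The late interview probably serves the oversampling of small-coupon buyers, which requires purchase to be known. That is a reason to keep the interview date. It does not justify treating the interview as pre-treatment.

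**Conclusion.** The schedule and the Section 6.1 estimator do not fit together for outcomes on 4-week recall and for current-status items. On average 90% of the 4-week window follows the draw, assuming evenly spread interviews. About 60%, 22.5% or 2.5% of it is already under cover if cover starts 2, 4 or 6 weeks after the draw.

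The bias is conditional. It is zero without an early effect, toward zero if the early effect has the sign of the later one, and away from zero if care is postponed. Its size cannot be fixed from the protocol, because neither the cover start date nor the early effect is given. For the same reason, calling the baseline already treated is justified for the coupon and the purchase opportunity, but not shown for effective cover. A statement that the whole ITT analysis is biased would go too far, since 12-month outcomes are little affected.

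**What to change.** 1. In Section 6.1, for 4-week and current-status outcomes, make the main ITT the large-versus-small coupon difference at follow-up within village meeting, in the main evaluation sample of Section 4. Adjust only for time-invariant or pre-meeting information. Entering the post-draw baseline value as a covariate would bring the same problem back.
2. Keep difference-in-differences for outcomes whose baseline window lies mainly before the draw. Record event dates and leave post-meeting events out of baseline values. A 12-month item then keeps 45 to 50 of its 52 weeks, whereas a 4-week item keeps nothing from week 4 on.
3. State when cover starts, and reconcile Sections 4 and 5.1 with the pre-lottery premise in the appendix (Table 4, equation (5) and part c).
4. In the take-up regressions, label attitudes and quality perceptions asked after purchase as descriptive.
5. Leave round 2 where it is. An earlier round would carry its 12-month window back before the draw: at week 48 it would reach week −4.

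**Cost.** Changes of wording, a date field per event, and some precision for the affected outcomes, because fixed effects no longer remove variation between households. With equal variance σ² per round and correlation ρ between rounds, a two-round difference has variance 2σ²(1 − ρ) per household, against σ² at follow-up alone. Precision is therefore lost only where ρ exceeds 0.5. The protocol does not give ρ.
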